As mentioned under the section for blinding, there will be two assessments of the MPS index score at T1 and T2, as dental staff are not blind to their second and third meeting with the prisoner. If the original examiner finds no improvement in the MPS-index score, the second examiner's score will be ignored. If the original examiner finds an improvement, the average score of the original examiner and the second examiner will be used, however the second examiner's score will not be used to increase the average score above the assessment of the original examiner. We consider this a conservative approach. If the original examiner is not part of the team that evaluates at T1 and T2 (for example if the prisoner has been transferred to a different prison, or due to sick absence), an average score of the two assessments by the new examiners will be used.

Another concern is potential differences in how oral examinations and the intervention is conducted across multiple sites. To minimize differences, all dental staff have undergone the same MI training and practice. All oral examinations are being conducted by trained professionals, and they have gone through a calibration day prior to the start of the data collection. Moreover, they will continuously be provided guidance from a professional MI-consultant. In addition, we track the time they spend on each MI-based conversation.

Recruitment of prisoners may also be slightly different from one prison to another, as in half of the prisons it is done by prison officers and the other half it is done by dental staff. Prisoners may perceive the question of whether they want to participate or not differently, depending on whether they are asked by a prison officer compared to a dental staff. Moreover, the language assessment may also be different. Although this occurs independent of the randomization, it might lead to a difference in the population recruited to the experiment across prisons. Unfortunately, we could not have the same recruiter across all prisons. However, the information provided to the prisoners is the same across all prisons. This also applies to the instructions concerning language assessment; in the case of uncertainty about Norwegian language skills, the same screening question is asked across prisons, and the same evaluation criteria is being used.

Conclusion

Conducting randomized controlled experiments in prison are challenging, especially during a pandemic. It requires solid external partners willing to adapt to unforeseen challenges that arise prior to and during data collection, and a research plan that likely need adjustment along the way to meet such challenges. This pre-analysis plan was written before any data analysis had been done, but after data collection was initiated. It therefore includes some of the initial unforeseen challenges the study faced, with prisons going into full lockdown due to the Omicron-variant of the Coronavirus flourishing in November and December 2021.

The pre-analysis plan includes detailed descriptions of the population, data collection and analytical decisions made prior to any analysis being conducted. It raises several issues that may arise during the data collection and data analysis, and how to cope with these issues if they arise. However,

conducting research on this population in such an institutional setting is still challenging, and unforeseen events may still arise.

References

Brand, V. S., Bray, K. K., MacNeill, S., Cately, D., Williams, K. (2012). Impact of single-session motivational interviewing on clinical outcomes following periodontal maintenance therapy. *International Journal Dental Hygiene*, 11(2), 134-141.

Hayes, S. (2002). Early Intervention or Early Incarceration? Using a Screening Test for Intellectual Disability in the Criminal Justice System. *Journal of Applied Research in Intellectual Disabilities*, 15(2), 120-128.

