All prisoners in the study undergo an oral examination to establish a baseline (hereafter T0) of oral health and a comprehensive questionnaire to identify risk factors and their attitude towards their oral health and oral treatment. Norwegian speaking prisoners are then randomized into either a treatment or control group. In the treatment group, dental staff initiate a conversation with the prisoner based on techniques from MI. Both groups finally receive a toilet bag with basic equipment to regularly clean their teeth. After 4 weeks and 12 weeks (hereafter T1 and T2), prisoners are invited back for another oral examination and a follow-up questionnaire, to measure changes in oral hygiene, oral cleaning routines, and attitude towards their oral health. At T1 we also conduct a screening of general learning difficulties using the validated screening tool HASI (Hayes, 2002). If the intervention proves to be an effective tool in improving oral hygiene, oral cleaning routines, and/or attitude towards own oral health, it can serve as an alternative proactive approach to improve oral health of a vulnerable group in society. If the improvements in oral hygiene and oral cleaning routines are long lasting, this may in turn lead to a reduced need of oral treatment. An improved attitude towards own oral health may, together with other rehabilitation programs in prison, improve the prisoner's self-esteem and chances to successfully returning to society after having served their prison sentence.

Study Design

Hypothesis:

H1: The conversation based on Motivating Interviewing (hereby the intervention) leads to a reduction in observed plaque and gingival inflammation for prisoners.

H2: The intervention leads to improved reported cleaning routines of prisoners in general, and particularly brushing of teeth.

H3: The intervention leads to a reduction in prisoners' intake of food and drinks in total, and particularly in-between meals.

H4: The intervention leads to improved perceptions about the prisoner's oral health. It improves how they view their oral health, they consider their oral health as more important, they report an increased wish to improve it, and they have increased efforts to improve it.

H5: The intervention leads to an increase in number of questions the prisoner asks during their visit with the dental staff, suggesting an increase in curiosity concerning their oral health.

Treatment effects and measurements:

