The main variable of interest and primary outcome measure of the treatment effect is the mucosal-plaque index (MPS). It consists of the sum of a four-point plaque score (PS) and a four-point mucosal score (MS). For the PS, score of 1 suggests no visible plaque, score of 2 suggests plaque is barely visible, score of 3 suggests a moderate amount of plaque, and score of 4 suggests large amount of plaque almost covering the whole surface of teeth. For the MS, score of 1 suggests normal mucosal, score of 2 suggests mild inflammation, score of 3 suggests medium inflammation, and score of 4 suggests strong inflammation. For both scores, if in doubt between 1 and 2, they are instructed to score 1. If in doubt between 3 and 4, they are instructed to score 4.

The index is designed to evaluate oral health and oral hygiene in groups of individuals, developed for use in institutions. This makes it a suitable index to be used when conditions are not optimal to assess the patient. In prison, dental staff have limited equipment and poor light compared to conditions at a dental clinic. It was therefore important to use an index designed to be used outside of dental clinics with less optimal conditions for oral examination.

The secondary measures of outcome are based on questionnaire responses. These are questions asked both prior to treatment and during the follow-up period, and measures changes in how the prisoner perceives his oral health, how his routines are for maintaining his teeth, and his intake of food and drinks. How these questions are formulated can be seen from the questionnaire directly. These questions are designed to measure behavioral changes because of the intervention. As the questions are identical at each meeting point, any difference in changes across the treatment and control group is likely to be a result of the intervention. Importantly, even though the MPS-index may not measure a significant change in oral hygiene, such behavioral changes may still be of great importance. For example, even though a prisoner does not change his cleaning routines and is unable to improve his plaque score, a reduction in intake of unhealthy food and drinks may still reduce the damage on his teeth. Likewise, an improved perception about their oral health, may still improve self-esteem, even though there is no reduction in plaque score.

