Prisoners are not informed whether they are in the treatment or control group and are therefore blind to treatment status. Dental staff are blind to prisoners' treatment status at the time of the first oral examination and questionnaire. The prisoner's treatment status is revealed just after this. Hence, dental staff collects all data prior to knowing the prisoner's treatment status, and only learn this when they start the MI-based conversation. When prisoners are back at T1 and T2 for follow-up oral examinations and questionnaires, dental staff might still remember whether the prisoner was treated or not. To partially account for potential bias in the oral examination (assessment of oral hygiene and inflammation in gingival), there are two independent assessments of this at T1 and T2. See pre-specification of analytical decisions for more on this.

Power calculations:

We have used GPower and Optimal Design to conduct power calculations.

GPower is used to calculate required sample size for simple comparison of means for the main variables of interest between the treatment and control group, without considering that data is collected at multiple sites. We choose the non-parametric Wilcoxon-Mann-Whitney test, set alpha to 0.05 and required power to 0.8. There is uncertainty concerning the effect size. Previous literature offers some guidance, however there are several important differences to our study. MI-interventions to change oral health have previously been tested on periodontist patients and patients with mental illness, populations that differ from ours. For our main variable of interest, level of plaque, these studies have found effect sizes ranging from 0.286 to 1.213¹. However, one should note that these studies have used different indexes to measure plaque, questioning the comparability of the effect sizes. Setting the power estimate to a moderate level in this range, to 0.5,

¹ An effect size of 0.286 was found after 12 weeks in Brand et al. (2012), whereas an effect size of 1.213 was found in Godard et al. (2011).

our required sample size is 106 prisoners. If we use a more conservative estimate and set it to the lowest effect size observed in the studies referred to above (0.286), the required sample size is 320.

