To test the overall effects of the intervention on our primary and secondary outcome variables, we will conduct non-parametric Wilcoxon Mann-Whitney U-tests. Given the ordinal outcome variables, we consider this test as more appropriate alternative relative to traditional two independent sample t-tests. We will compare the means of the treatment group and the control group at T0, T1 and T2. At T0 we expect no differences in means as no intervention has occurred. At T1 and T2 we expect better scores for the treatment group relative to the control group. Notably, our primary interest will be the difference in means at T1, as we expect more missing data at T2 due to prisoners being released from prison. However, for the intervention to have a long-lasting improvement on the prisoner's oral health, it is important that the intervention successfully enables the prisoner to make lasting changes. If we do not find a statistical difference between the treatment and the control group at T2, however, it may be hard to tell whether this is due to the intervention effect fading out or lack of power. See power analysis for more details on this, in which we show effect sizes possible to detect at different number of observations, given that power is set to 0.8 and number of sites is set to 4. As drop-out increases at T2, the higher the effect size must be for us to be able to detect any statistical difference between the groups.

Moreover, we are going to run multiple ordinal logistic regressions where we include selected covariates (see below). Running regressions allow us to control for the baseline measures of plaque

by using the baseline score of the outcome variables as a lagged dependent variable, in addition to including other covariates likely to correlate with the treatment and to explain variation in the dependent variable. For robustness purposes we also run regressions with fixed effects, controlling for unobserved individual time-invariant characteristics.

Covariates:

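### The plan's and/or wording lets effectiveness be concluded from secondary outcomes without any control of multiplicity, although MPS at T1 is already named as primary

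*Combined protocol and SAP*

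**What the plan says.** The plan is one document. Under *Treatment effects and measurements* it names MPS as the primary outcome and makes the questionnaire outcomes and the count of questions asked secondary. *Statistical model specification* gives T1 as the comparison of primary interest and warns that a null result at T2 will be hard to interpret.

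Three passages loosen that structure:

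- *Project summary*: the intervention could become an alternative approach for this population if it is effective "in improving oral hygiene, oral cleaning routines, and/or attitude towards own oral health".
- *Treatment effects and measurements*: "even though the MPS-index may not measure a significant change in oral hygiene, such behavioral changes may still be of great importance". Two examples of benefit without a plaque improvement follow, one on diet and one on self-esteem.
- *Statistical model specification*: "To test the overall effects of the intervention on our primary and secondary outcome variables, we will conduct non-parametric Wilcoxon Mann-Whitney U-tests". Both follow-up visits are tested, and ordinal logistic and fixed-effects regressions come after.

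*Hypothesis* lists H1 to H5; H4 alone covers four separate perceptions or behaviours. There is no multiplicity adjustment, testing order, supportive-only label or formal success criterion. A significance level appears only under *Power calculations* ("set alpha to 0.05 and required power to 0.8"), with no statement of one- or two-sided testing.

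**The concern.** Naming one primary outcome protects a claim about that outcome. It does not protect a claim resting on something else, and the summary sentence is the plan's main link between results and a conclusion about usefulness. That link is disjunctive.

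The case in which this matters is realistic. The plan expects appreciable attrition and an uncertain effect size, so MPS may well miss significance. A report could then call the intervention effective because one questionnaire item favoured treatment, and nothing in the plan would mark that as weaker evidence. What is at stake is an ineffective conversation being put forward as a useful prison programme.

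**Working it through.** **1. The plan's own sample sizes, to see which test they imply.** Inputs from *Power calculations*: "We choose the non-parametric Wilcoxon-Mann-Whitney test"; alpha 0.05; power 0.8; "Setting the power estimate to a moderate level in this range, to 0.5"; and "our required sample size is 106 prisoners". The conservative case is effect size 0.286 with 320 prisoners. Allocation is 1:1 (*Randomization*).

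Normal approximation, per group: n = 2(z_alpha + z_power)² / d², divided by the Wilcoxon efficiency 3/π = 0.955.

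- One-sided, d = 0.5: 2(1.645 + 0.842)² / 0.25 = 49.5, so 50. Then 50 / 0.955 = 52.4, so 53 per group, **106 in total**.
- One-sided, d = 0.286: 152 / 0.955 = 159.2, so 160 per group, **320 in total**.
- Two-sided, using the noncentral t: 134 and 404. Two-sided power at 106 and 320 is about 0.70 in both cases.

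Other parent distributions and a plain t-test did not reproduce 106 or 320 with either sidedness. The stated numbers therefore fit a one-sided 0.05 test. That agrees with the directional expectation "At T1 and T2 we expect better scores for the treatment group relative to the control group", but the plan does not declare it.

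**2. What is counted.** Only outcomes visible in the document:

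- 3: the domains in the summary sentence.
- 5: hypotheses H1 to H5, one test each.
- 8: MPS, brushing, between-meal intake, four H4 items, questions asked.
- 16: those eight at both T1 and T2.

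The questionnaire is not in the document, so the true item count is unknown. The regressions are not counted.

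**3. Chance of at least one favourable significant result when nothing works.** Only a favourable result can lead to a claim of effectiveness, so each test contributes 0.05 if one-sided and 0.025 if two-sided at 0.05. For k independent tests the chance is 1 − (1 − a)^k. For example, 1 − 0.95³ = 0.143, 1 − 0.95⁵ = 0.226 and 1 − 0.95⁸ = 0.337; 1 − 0.975³ = 0.073, 1 − 0.975⁵ = 0.119 and 1 − 0.975⁸ = 0.183. Correlated values come from 400,000 simulated sets of equally correlated normal test statistics.

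| Tests | One-sided 0.05, independent | One-sided 0.05, correlation 0.7 | Two-sided 0.05, favourable only, independent | Two-sided 0.05, favourable only, correlation 0.7 |
|---|---|---|---|---|
| 3 | 14.3% | 10.3% | 7.3% | 5.5% |
| 5 | 22.6% | 13.5% | 11.9% | 7.4% |
| 8 | 33.7% | 16.7% | 18.3% | 9.5% |
| 16 | 56.0% | 22.3% | 33.3% | 13.1% |

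The reference value for a single test is 5% in the one-sided columns and 2.5% in the two-sided ones. At correlation 0.8, three domains tested two-sided give 4.9%, so the mildest scenario is no worse than a nominal 5%. Equal correlation is a simplification for the 16-test row, where the same outcome at two visits will be more closely related than different outcomes.

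**4. With the conclusion tied to MPS at T1.** One test decides, so the false-success chance is the declared alpha, and 106 and 320 stand on the plan's implied one-sided basis. If any of three domains were to count under Bonferroni, the one-sided totals would rise to 152 and 454; for five hypotheses, to 172 and 518.

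**The case against.** The strongest reply is that the main protection is already there: one primary outcome, one time point of primary interest, and everything else labelled secondary. On that reading the summary sentence explains why the trial is worth doing, and the passage on behavioural change explains why secondary outcomes are measured. Neither sets a threshold or says that one significant item is enough. This stands, and it limits the point to wording and interpretation.

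A reader might go further and infer three things that the document does not support:

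- *That the plan has a formal any-outcome success rule.* It does not. The and/or joins three domains in a conditional sentence about possible usefulness.
- *That every test is specified at 0.05.* That level is given only for the power calculations; the analysis section gives none.
- *That the error is necessarily far above 5%.* This depends on the number of tests, their correlation and sidedness. Counting two-sided significance in either direction inflates the figure, because it treats results that favour control as false successes. For ten tests at correlation 0.5 that count gives 28.6%, against 14.4% when only favourable results count.

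What survives is that no statement elsewhere prevents a conclusion from being drawn as the summary words it.

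**Conclusion.** The concern holds in a limited form. The plan identifies its primary outcome and main time point, but its wording leaves room to conclude effectiveness from secondary outcomes, and no multiplicity control covers that route.

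Taking one test per domain or hypothesis, with correlation between 0 and 0.7, the false-success chance is about 10% to 23% if tests are one-sided at 0.05. It is about 5.5% to 12% if they are two-sided and only favourable results count. With eight named outcomes the ranges are 17% to 34% and 9.5% to 18%, and they are higher if T2 counts as well.

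These figures assume that each outcome is tested at 0.05, that any one favourable result may support the claim, and that the item counts and correlations are as set out in the working. None of these is fixed by the document. A claim resting on MPS at T1 alone is not affected.

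**What to change.** Before any analysis, in a dated amendment:

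1. State that the conclusion of effectiveness rests on MPS at T1.
2. List the H2-H5 outcomes from the questionnaire and report them at T1 as one secondary family with Holm-adjusted p-values, or label them supportive with no claim of effectiveness. Holm controls error within that family; the effectiveness conclusion keeps the declared alpha because it rests on MPS alone.
3. Treat T2 as supportive.
4. Reword the and/or sentence in *Project summary* and the sentence on behavioural change in *Treatment effects and measurements* to match.
5. As a separate item, state the alpha and sidedness actually used. If two-sided 0.05 is declared, say that power at 106 and 320 falls to about 0.70, and that 134 and 404 would be needed for 0.8.

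Items 1 to 4 need only wording and adjusted p-values, and they leave the power of the primary test unchanged. Their downside is lower power for individual secondary items if Holm is used. Item 5 can affect the primary test, which is why it should be decided openly and apart from the multiplicity change. Overall this is a cheap improvement.

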In addition, as a secondary outcome measure, dental staff take notes of how many times the prisoner asks questions about his teeth. If the intervention successfully increases the prisoner's interest in his own oral health, we could expect more questions about his oral health.

Basic methodology:

The study is a randomized control trial (RCT), testing an MI-based intervention on oral health (oral hygiene) for prisoners in Rogaland County, Norway. More details about the population and the intervention follows in subsequent sections.

We randomize prisoners into treatment or control groups, blocking at prison level, using the randomization tool at www.randomizer.org. See the randomization section for more details on the randomization process. Moreover, we blind prisoners from treatment status, and dental staff is either blind to treatment when doing the oral examinations, or the oral examination is conducted by two dental staff independently of each other. See the blinding section for more details on blinding.

Study design and procedures:

Geographic region

The geographic region of this study is Rogaland County in southwestern part of Norway. Rogaland County is the wealthiest county in Norway measured in terms of household income (2019, SSB). Despite being one of the wealthiest counties in Norway, growing up in Rogaland is similar to growing up in other counties in Norway. An important reason for this is the unitary and federally funded school system, with only a few ideological or pedagogical based private schools. This gives all children growing up in Norway similar opportunities to obtain an education and subsequently enter the labor market.

Research population

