Clinical data will include information on decayed, missing and filled teeth (DMFT). This data will only be collected at T0, as it is not possible to observe any change during the follow-up period. Moreover, we will collect clinical data on plaque and mucosal inflammation, using the MPS index. This is our main variable of interest. Plaque is affected by oral hygiene routines and the intake of drinks and food that can damage teeth, and thus any observed difference in changes in plaque between the treatment group and the control group may be interpreted as an effect of the intervention. Dental staff has undergone a calibration exercise of both DMFT and MPS.

The questionnaire is extensive. It starts with some background questions about demographic and socio-economic status, which are not likely to change during the follow-up period, and thus only asked at T0. Next, we ask questions about their views on their own oral health. In particular, we ask them about how they perceive the condition of their own oral health, whether they want to improve it, whether they regularly visit a dentist outside of prison, their cleaning routines and their intake of food and drinks. Some of these questions are secondary variables of interest. In the case of an intervention effect, prisoners may have an adjusted view on their oral health, and they may change their oral cleaning routines and intake of food and drinks. We also ask them standardized questionnaires about their oral-health quality of life (OHIP-14) and their self-reported anxiety and discomfort to dental treatment (Corah). As these are unlikely to change during the follow-up period, they are only asked at T0.

We also collect data on their general physical and mental health. To measure mental health, we use the standardized questionnaire Mental Health Inventory 5 (MHI-5). We conduct the MHI-5 questionnaire at all meeting points, T0, T1 and T2, as we expect reduced effects of the intervention if they are experiencing worsened mental health. This may be important when studying heterogeneous effects of the intervention. Lastly, we collect data on their alcohol and drug use (outside of prison), using the short versions of alcohol use disorders identification test (AUDIT-4) and the drug use disorders identification test (DUDIT), collected only at T0.

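### H1 names both plaque and gingival inflammation but only their sum (MPS) is tested, so a significant MPS could be read as supporting both, and a plaque-only effect is diluted

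*Combined protocol and SAP*

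**What the plan says.** Under Study Design, Hypothesis, H1 says that the intervention "leads to a reduction in observed plaque and gingival inflammation for prisoners".

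Under Treatment effects and measurements, the outcome is defined: "The main variable of interest and primary outcome measure of the treatment effect is the mucosal-plaque index (MPS"), and "It consists of the sum of a four-point plaque score (PS) and a four-point mucosal score (MS"). The secondary outcomes follow in the same section. One group is from the questionnaire ("The secondary measures of outcome are based on questionnaire responses"), and the other is a count ("as a secondary outcome measure, dental staff take notes of how many times the prisoner asks questions about his teeth"). PS and MS are in neither group.

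Under Statistical model specification, the tests are limited to these outcomes: "To test the overall effects of the intervention on our primary and secondary outcome variables, we will conduct non-parametric Wilcoxon Mann-Whitney U-tests". On timing, "our primary interest will be the difference in means at T1". Under Covariates, the main adjustment variable is baseline MPS. Under Other issues, the rule for combining two examiners at T1 and T2 is written for the MPS score.

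Elsewhere the plan treats the index and one of its components as interchangeable. Data collection and sources of data names MPS as the main variable and then says that "any observed difference in changes in plaque between the treatment group and the control group may be interpreted as an effect of the intervention". Power calculations describes the main variable as plaque level and takes its effect sizes from plaque studies.

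**The concern.** The hypothesis and the test do not match. A sum can shift because one component shifts, so a significant MPS supports a lower combined score and nothing more specific. It cannot show that inflammation fell, yet H1 as worded invites that reading.

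The mismatch also works in the other direction. If the conversation changes brushing and plaque responds but inflammation does not, adding an unaffected MS adds variance without signal. The effect on MPS is then smaller than the effect on plaque. With no planned PS analysis, a real plaque effect could be missed, or could surface only as an unplanned analysis.

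**Working it through.** **Inputs from the plan.** Alpha 0.05, power 0.8, Wilcoxon-Mann-Whitney test; 106 prisoners for effect size 0.5 and 320 for 0.286 (Power calculations); 1:1 allocation in blocks of four (Randomization).

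**Assumptions not in the plan.** PS-MS correlation ρ of 0.3 to 0.7; equal component SDs (formula in step 2); four-point scores cut from a normal latent scale at 20/55/85% (simulation in step 3); an effect on plaque and none on inflammation.

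**Step 1: the plan's own figures.** With asymptotic relative efficiency 3/π = 0.955, the normal approximation for a one-sided test is N = 4(1.645 + 0.842)² / (0.955 d²). This gives about 104 at d = 0.5 and 317 at d = 0.286. The noncentral-t version gives exactly 106 and 320. Two-sided it gives 134 and 404, so the stated figures reproduce only one-sided, and the plan does not state sidedness. That is a separate matter; I use two-sided tests below and give the one-sided results where they matter.

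**Step 2: dilution by formula.** If both components have SD σ, Var(PS + MS) = 2σ²(1 + ρ). A plaque-only shift of dσ is then a standardised effect on the sum of d / √(2 + 2ρ).

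| Plaque effect | ρ = 0.3 | ρ = 0.7 |
|---|---|---|
| 0.5 | 0.5/√2.6 = 0.310 | 0.5/√3.4 = 0.271 |
| 0.286 | 0.286/√2.6 = 0.177 | 0.286/√3.4 = 0.155 |

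At the plan's pairings (0.5 with 106, 0.286 with 320), power for the sum is 34% to 27% two-sided, or 46% to 39% one-sided. For 80% one-sided power on the sum, the total would be 272 to 354 in place of 106, and 826 to 1,078 in place of 320.

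**Step 3: simulation on the four-point scores.** Two-sided 0.05 Mann-Whitney tests, ρ = 0.3 to 0.7:

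| Plaque-only effect (latent SD) and N | MPS significant | PS alone | MS alone |
|---|---|---|---|
| 0.5 with 106; 0.286 with 320 | about 25-32% | about 63-70% | about 5% |
| 0.5 with 320 to 400 | about 60-82% | above 98% | about 5% |

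The MS column is the test's error rate, because no MS effect was put in; about half of those rejections favour treatment. A different set of cut-points (quartiles) at ρ = 0.5 gave 27% for MPS at 0.5 with 106, 28% at 0.286 with 320, and 66% at 0.5 with 320, so the pattern does not hang on the cut-points.

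**Step 4: can PS and MS simply be tabulated?** Not quite, because the two-examiner rule is triggered by improvement in the total. Take baseline PS 3, MS 3; original examiner 2 and 3; second examiner 3 and 2. The original total fell from 6 to 5, so the totals are averaged: (5 + 5)/2 = 5. Apply the rule to each component instead, reading its cap as a limit on credited improvement. PS improved, so it averages to 2.5; MS did not, so it stays 3. The sum is 5.5, which is not the analysed MPS of 5. A component-level convention is needed.

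**The case against.** H1 can fairly be read as spelling out what MPS covers, since the plan says data on plaque and on mucosal inflammation are gathered through that index. MPS is a legitimate primary, and no primary test or error rate is wrong on this account. This stands, and it is why the remedy leaves the primary alone.

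A reader might infer that the plan will report a significant MPS as confirming both parts of H1. The documents do not support that: no section gives a decision rule for H1. Where the wording is loose it leans towards plaque, not towards claims about inflammation. What the text supports is that a significant MPS could be read either way, because the plan does not settle it.

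A reader might also worry that plaque and inflammation could move in opposite directions and cancel. Nothing in the documents suggests this, and it forms no part of the point.

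Finally, 60-82% should not be taken as the expected size. It combines the 0.5 effect with 320 to 400 analysed, whereas the plan pairs 0.5 with 106. The 400 corresponds to the assumed 100 recruits in each of four prisons, and the plan expects fairly high attrition and notes that the smallest prison has 18 rooms. At the plan's own pairings a plaque-only effect is more often missed than found, so dilution matters at least as much as over-reading.

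**Conclusion.** The point holds in this form. H1 makes a joint claim, only the sum is planned for testing, and the sum can neither establish the inflammation part nor detect a plaque-only effect efficiently. At the plan's own pairings such an effect makes MPS significant in about 25-32% of trials, against about 63-70% for PS alone. With a 0.5 effect and 320 to 400 analysed, MPS is significant in about 60-82% with inflammation unchanged.

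The percentages depend on the assumed correlation, score distribution and plaque-only scenario. The qualitative conclusion does not: it follows from the outcome being a sum. This is a gap in specification that leaves the primary analysis intact, and closing it is a cheap improvement.

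**What to change.** 1. Keep MPS at T1 as the sole primary outcome.
2. Word H1 as a reduction in the MPS index, and use that term wherever the plan now says plaque but means MPS.
3. Pre-specify PS and MS at T1 as supportive analyses, using the same Mann-Whitney test and ordinal regression, each adjusted for its own baseline score. Claim an effect on plaque or on inflammation separately only if that component's own result supports it.
4. State how the two-examiner rule carries over to the components. One option is to let the total MPS decide whether the original examiner's scores or the averaged scores are used, and then use that choice for both components. In the example above this gives PS 2.5 and MS 2.5, which add up to the analysed MPS of 5.

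**Cost.** Two supportive analyses, labelled as not controlling the primary error rate, and a sentence on the examiner rule. Both components must already be scored to form MPS, so no further examination or participant is needed, provided the two scores are kept separately. The Conclusion says the plan was written before any data analysis; the change should likewise be made and dated before outcome data are analysed.
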